1. SUMMARY

Rationale

The worldwide practice of fluid and vasopressor therapy in critically ill invasively ventilated patients is uncertain. Indeed, it is unclear whether there is a difference in fluid and vasopressor therapy in these patients between Low- and Middle-income Countries (LMICs) and High-income Countries (HICs).

Objective

To determine various aspects of fluid and vasopressor therapy in critically ill invasively ventilated patients in LMICs and HICs.

Hypothesis

There is substantial worldwide variation in practice of fluid and vasopressor therapy in critically ill invasively ventilated patients.

Study design

International, multicenter, observational study in critically ill invasively ventilated patients; data are captured during a predefined period per geographic region or country.

Study population

Critically ill invasively ventilated patients.

Main study parameter/endpoint

The primary outcome is a composite of various aspects of fluid therapy, including total volumes of types of fluids administered in the first three days after start of invasive ventilation and total volume of fluids infused in the first seven days after start of invasive ventilation. Secondary outcomes include timing of start, type, and duration of continuous administration of vasopressors; timing of start, infusion time and types of administered diuretics; daily urine output and cumulative fluid balances; and typical ICU outcomes, like duration of ventilation, lengths of stay in ICU and hospital, and mortality in the ICU and hospital, and at day-28, -60 and -90.

Nature and extent of the burden and risks associated with participation, benefit and group relatedness

Because of the observational design of the study using routinely collected data, there is no additional burden for the patient. Collection of data from ICU charts or electronic medical records systems is of no risk to the patients.

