5.5. Sample size calculation

No formal sample size calculation is necessary for the primary endpoint. However, for investigating associations of aspects of fluid and vasopressor therapy with mortality using logistic regression and adjusting for a limited set of pre-specified confounders, we estimate to need 150 ‘events’ using the 10 event per variable rule of thumb. As fluid and vasopressor management is particularly important in patients with acute respiratory distress (ARDS), we will need at least 150 events in this subgroup. With an incidence of ARDS of approximately 20% and a mortality rate of 30%, we estimate to need 2500 patients to have 150 events in patients with ARDS (37). Assuming that a participating ICU has 50 unique admissions in 4 weeks on average, of which 25% is invasively ventilated for > 24 hours, we expect to need a minimum of 200 participating ICUs (38-40).

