6.2. Study procedures

Patients in participating centers are screened on a daily basis. Eligible patients are included during the 28–day observation period, from Monday at 8:00 AM to the Monday four weeks later at 7:59 AM (in time zones of the participating centers). The timing of the 28–day observation period will be flexible for participating centers and determined at a later stage together with the international study–coordinator and each national investigator. Times points of data collection:

- Demographic and baseline data are collected from the clinical files – at ICU admission;
- Types, quantities, of administered fluids– during the first three calendar days with high-granularity. From day 4-7 lower granularity data concerning the total volume of infused fluids will be collected;
- Types and modalities of administration of vasopressors – over a maximum of seven days of ICU admission;
- Vital signs, laboratory results and limited treatment parameters are collected – once daily for a maximum of seven days;
- Cumulative fluid balance – calculated once a day on a time point convenient per each center for a maximum of seven days; and
- Outcomes – recorded at 90 days, the day of death or hospital discharge, whichever comes first.

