6.2.3. Data to be collected

The following data will be collected for all enrolled patients admitted to ICU during the screening period. Day 0 is defined as the day of initiation of invasive ventilation. Day 1 is defined as the first full calendar day after initiation of invasive ventilation. In patients that are not invasively ventilated at ICU admission day -3 to -1 are defined as the days before intubation but after ICU admission.

A. At ICU admission;

- Gender, male/female/other;
- Age, years;
- Weight, kg;
- Length, cm;
- Ethnicity, Black, East Asian, Indigenous (First Nations, Inuk/Inuit, Métis), Latin American, Middle Eastern, South Asian, Southeast Asian, White;
- Reason for ICU admission;
- Traumatic brain injury?;
- Sub-arachnoid hemorrhage?
- Date of ICU admission;
- Date of start of invasive ventilation;
- Did the patient receive non-invasive ventilation or high-flow nasal oxygen prior to intubation, if so: on which day?;
- Serum creatinine, $\mu\text{mol/L}$ or mg/dL , lowest in the last year, if available; and
- If the reason for ICU admission was burns: what was the cause of the burn and how much total body surface area is affected by the burns
- If the reason for ICU admission was sepsis, what was the focus of the sepsis (e.g. respiratory, abdominal)

B. On day 0;

- Type and volume, ml, of each fluid infusion (including medication and parenteral nutrition);
- Type and volume of oral fluids;
- Anuria ≥ 12 hours?, yes/no;
- Urine output, ml, over 24 hours;
- Extracorporeal life support, venoarterial/venovenous/no;

- Renal replacement therapy, yes/no, if yes;
 - Volume extracted by ultrafiltration, ml, over 24 hours;
- Cumulative fluid balance, ml;
- Loop diuretics given, yes/no, if yes;
 - Furosemide, yes/no, if yes;
 - (if no furosemide used) Bumetanide, yes/no, if yes;
 - (if no bumetanide or furosemide used) Torasemide, yes/no, if yes;
 - (if no Torasemide, bumetanide, furosemide used) Edecrin, yes/no;
- Additional diuretic given (thiazide, carbonic anhydrase inhibitor or mineralocorticoid antagonist), yes/no;
- Serum creatinine, $\mu\text{mol/L}$ or mg/dL , at a convenient fixed time point;
- Serum hemoglobin, $\mu\text{mol/L}$ or mg/dL , at a convenient fixed time point;
- Serum albumin, at a convenient fixed time point;
- Vasopressors initiated, yes/no, if yes;
 - Time between ICU admission and initiation of vasopressors, hours;
 - Drug(s) used as vasopressor;
- Mean arterial pressure (MAP) mmHg, at a convenient fixed time point;

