- Arterial or venous lactate, mmol/L , at a convenient fixed time point;
- Serum sodium, mmol/l , at a convenient fixed time point;

- Serum chloride, mmol/l, at a convenient fixed time point;
-
- S(c)VO₂, mmol/L, highest and lowest value;
- PaO₂, kPa or mmHg, at a convenient fixed time point;
- (if no PaO₂ is known) Peripheral arterial oxygen saturation (SpO₂), percentage, at a convenient fixed time point;
- Inspired oxygen fraction, %, at time of PaO₂ or (if no PaO₂ is known) SpO₂;
- Was there new-onset (<7 days) respiratory symptoms, or acute worsening of respiratory symptoms?, yes/no, if yes;
- Are there bilateral opacities on chest imaging (including lung ultrasound), yes/no;
- If there was hypoxemia, was the hypoxemia explained by cardiac failure, yes/no?
- Richmond Agitation Sedation Scale (RASS), highest value of the day; and
- SOFA score.

D. Daily on day 3 to 7 or ICU discharge; and on day -1, day -2 and day -3;

- Total volume of infused fluid, ml, over 24 hours
- Cumulative fluid balance, ml, over 24 hours;
- Urine output, ml, over 24 hours;
- Extracorporeal life support, venoarterial/venovenous/no;
- Renal replacement therapy, yes/no, if yes;
 - Volume extracted by ultrafiltration, ml, over 24 hours;
- Loop diuretics given, yes/no, if yes;
 - Furosemide, yes/no, if no;
 - (if no furosemide used) Bumetanide, yes/no, if no;
 - (if no bumetanide or furosemide used) Torasemide, yes/no;
 - (if no Torasemide, bumetanide, furosemide used) Edecrin, yes/no;
 - Additional diuretic given (thiazide, carbonic anhydrase inhibitor or mineralocorticoid antagonist), yes/no;
- Serum creatinine, µmol/L or mg/dL, at a convenient fixed time point;
- Serum hemoglobin, µmol/L or mg/dL, at a convenient fixed time point;
- Serum albumin, at a convenient fixed time point;
- Vasopressors used, yes/no, if yes;
 - Drug(s) used as vasopressor;

- MAP, mmHg, at a convenient fixed time point;
- Heart rate, beats/min, at a convenient fixed time point
- Atrial fibrillation or flutter during the last day, yes/no;
- Arterial or venous lactate, mmol/L, at a convenient fixed time point;
- Serum sodium, mmol/l, at a convenient fixed time point;
- Serum chloride, mmol/l, at a convenient fixed time point;
- PaO₂, kPa or mmHg, at a convenient fixed time point;
- (if no PaO₂ is known)) Peripheral arterial oxygen saturation (SpO₂), percentage, at a convenient fixed time point;
- Inspired oxygen fraction, %, at time of PaO₂ or (if no PaO₂ is known) SpO₂; and
- SOFA score.

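### The 7-day fluid total in the primary outcome has no rule for death or ICU exit, and its day window is stated in conflicting ways, so it partly measures ICU stay

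*Protocol*

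**What the plan says.** The Summary describes the primary outcome as a composite. Two components are named. One, by type of fluid, is the "total volumes of types of fluids administered in the first three days after start of invasive ventilation"; the other, for all fluid together, is the "total volume of fluids infused in the first seven days after start of invasive ventilation". Both are totals, and neither has a denominator. Section 6.1.1 lists the primary parameter more loosely, as quantity, timing and type of intravenous fluid.

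The data behind these totals are set out in two places:

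- Section 6.2 has detailed fluid data for three calendar days, and then: "From day 4-7 lower granularity data concerning the total volume of infused fluids will be collected".
- Section 6.2.3 fixes the start of the count: "Day 0 is defined as the day of initiation of invasive ventilation". For the day that comes next it says: "Day 1 is defined as the first full calendar day after initiation of invasive ventilation". Volumes by fluid type are listed for day 0 and for days 1 and 2. The total infused volume is then listed as "Daily on day 3 to 7 or ICU discharge".

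Section 6.2.3 records the "Date of start of invasive ventilation" and the dates of ICU admission, ICU discharge and death. No clock time is listed for any of these.

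Section 8.2 excludes patients transferred to another ICU in the first three calendar days of ICU admission. Patients transferred after that but before seven days are excluded from the secondary endpoints only. Death and discharge to the ward within the window are not mentioned.

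**The concern.** A total over a fixed window is comparable between patients only if all are observed for the whole window, or if the plan says what a shorter observation means. Here collection ends when the patient leaves the ICU, and necessarily also at death. At the same daily rate, a patient who leaves on day 3 has a smaller 7-day total than one who stays.

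The primary hypothesis (section 3.2) is that practice varies widely, and comparing LMICs with HICs is a stated aim (section 3.1). If ICU stay or early mortality differs between ICUs or income groups, the 7-day total will differ even where fluid practice is the same. The conflicting day ranges add a second problem: two analysts could sum different days and both claim to follow the protocol.

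**Working it through.** **1. The plan's own figures.** Section 5.5 reproduces: 150 / (0.20 × 0.30) = 2500 patients, and 2500 / (50 × 0.25) = 200 ICUs. This point does not affect them.

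**2. The window.** Section 6.2 read as days 1-3 and then 4-7 gives 3 + 4 = 7 days. Section 6.2.3 gives days 0-2 and then 3-7, which is 3 + 5 = 8 calendar days. The Summary says seven days after start of ventilation. Time after start of ventilation, for a patient who stays throughout:

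| Days summed | Shortest | Longest |
|---|---|---|
| 0-2 | 48 h | 72 h |
| 0-6 | 144 h | 168 h |
| 0-7 | 168 h | 192 h |

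The spread within each row comes from the clock time of intubation on day 0. If start times are uniform over the day, its SD is 24/√12 = 6.9 h, or 6.9/60 = 11.5% of the 60 h mean for days 0-2. Nor is day-0 volume restricted to fluid given after intubation, although the day-0 sedation score is. A patient already in the ICU the day before may contribute a full day 0, part of it before ventilation started.

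**3. The transfer rule.** The 7-day volume is a primary component. Excluding later transfers from the secondary endpoints alone therefore leaves their truncated totals in the primary analysis.

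**4. Size, by example.** All inputs here are assumptions: constant 2.5 L/day in both groups; time in ICU after start of ventilation T = 1 + an exponential with mean 9 or 5 days, so mean stays of 10 and 6 days. Expected observed days within a window of w days are 1 + m(1 − e^(−(w−1)/m)), with m the exponential mean.

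- w = 7, m = 9: 1 + 9(1 − e^(−6/9)) = 5.38 days; × 2.5 = 13.4 L
- w = 7, m = 5: 1 + 5(1 − e^(−6/5)) = 4.49 days; × 2.5 = 11.2 L
- w = 3, m = 9: 1 + 9(1 − e^(−2/9)) = 2.79 days; × 2.5 = 6.98 L
- w = 3, m = 5: 1 + 5(1 − e^(−2/5)) = 2.65 days; × 2.5 = 6.62 L

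Identical practice thus differs by about 20% on the 7-day total and about 5% on the 3-day total.

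**5. Size, by simulation.** Assumed inputs: mean 3 L/day with coefficient of variation 0.4; 30% mortality (section 5.5 gives 30% for ARDS only); 30-70% of those who die and 20-60% of survivors out of the ICU by day 7; volumes summed over days 0-2 and 0-7. Observed time then explains 52-67% of the log-variance of the 7-day total and 14-22% of that of the 3-day total.

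**The case against.** The best defence is that the volume actually received is a legitimate descriptive quantity, that section 8.2 promises a full SAP before each analysis, and that volumes are collected daily. Per-day summaries can therefore be produced without changing the design. Days 0-7 contain days 0-6, so a 7-day total can be formed once someone decides which days count. Much of this stands: the truncation can be handled with data already planned. It does not remove the point, because the outcome definition and the list of data items are protocol content, and as written they conflict. A SAP also cannot recover clock times that were never recorded.

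A rate is not a complete answer either. If fluid is front-loaded, for example 4, 3, 2.5, 2, 2, 2, 2 L (assumed), identical practice gives 9.5/3 = 3.17 L/day for a 3-day stay and 17.5/7 = 2.5 L/day for a 7-day stay.

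A reader might go further and infer three things that the protocol does not support:

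- **That the planned mortality associations suffer immortal-time bias.** Section 5.5 speaks only of "investigating associations of aspects of fluid and vasopressor therapy with mortality using logistic regression". No section makes a 3- or 7-day total the exposure or sets a Cox time origin, and landmarking or time-varying exposure is ordinary SAP content. The concern applies only if such a total is used. In the simulation above, with no true effect, the unadjusted odds ratio for death per litre of the 7-day total ran from 0.94 to 1.03, its direction depending on whether early death or early discharge dominated.
- **That the partial day 0 brings in survival or length of stay.** It reflects the hour of intubation, so it adds noise and ambiguity.
- **That the criterion of more than 24 hours of ventilation cannot be verified.** Local investigators screen patients daily with the charts at hand; the criterion need not be recomputable from dates in the CRF.

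**Conclusion.** The point holds for the 7-day component of the primary outcome and for the definition of the window. As written, the 7-day total combines fluid practice with time in the ICU, later ICU-to-ICU transfers enter it truncated, and the sections disagree on which days it covers. The 3-day totals are affected only slightly.

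These textual findings rest on no assumption. The size does: the protocol gives no distribution of ICU stay, death or discharge times, so the 20% and 5% differences and the variance shares are illustrations. A difference in observed time between the groups compared is what shifts the LMIC-HIC contrast; if observed time is alike, that contrast is little affected, although variation between patients still includes it.

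**What to change.** 1. State one window for each component, for example days 0-2 and days 0-6, and reconcile section 6.2 and the Summary with section 6.2.3. Say whether day-0 volume includes fluid given before intubation.
2. Beside the 7-day total, report volume by study day among patients still in the ICU, and volume per observed ICU day, with the observed time. The by-day figures are needed because a single rate still depends on stay when fluid is front-loaded.
3. Apply the rule for transfers between the third and seventh day to the 7-day primary volume too, and state how death and ward discharge within the window are handled.
4. Add clock times for ICU admission and start of ventilation, and for ICU exit if an hourly denominator is wanted.
5. If a multi-day total is used as an exposure for mortality, use a landmark at the end of the exposure window, or daily fluids as a time-varying covariate.

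The cost is two or three CRF time fields, some protocol wording and a little more analysis. A landmark would drop patients who die or leave before it from that association analysis only.

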2. INTRODUCTION AND RATIONALE

2.1. Temporal changes in fluid therapy in critically ill invasively ventilated patients

Intravenous fluid is among the most prescribed medications in the intensive care unit (ICU). Most is used intentionally, to improve hemodynamics in patients with hypotension or hypoperfusion, and to compensate for lost fluids (1). A smaller amount is administered unintentionally, as a vehicle for medication or to maintain catheter patency (2). Intravenous fluid administration was once considered to be ‘harmless’. However, in recent years it became clear that fluid therapy has important side-effects. The paradigm of ‘liberal fluid administration’ in critically ill patients has been challenged, and novel concepts such as ‘restricted fluid administration’, defined as minimizing fluid intake while maintaining organ perfusion (3), ‘timely deresuscitation’, defined as early and active removal of fluid after initial resuscitation (4), and ‘fluid tolerance’, defined as the degree to which a patient can tolerate fluid administration without causing organ dysfunction (5-7), were introduced.

As there are complex interactions between invasive ventilation and fluid status, fluid therapy in invasively ventilated patients is even more challenging. Invasive ventilation disrupts fluid homeostasis and predisposes to hemodynamic intolerance of hypovolemia (8). Conversely, hypervolemia can lead to pulmonary edema resulting in an impaired gas-exchange and worsened pulmonary compliance, jeopardizing lung-protective ventilation (8).

The type of fluid has also been subject of discussion. While initially thought to be beneficial, synthetic colloidal solutions not only have no benefit over crystalloid solutions (9-11), but even cause harm (12). Albumin solutions also have no benefit in unselected critically ill patients, and may only improve outcome in patients with septic shock but are considered harmful in patients with traumatic brain injury (13, 14). Crystalloid solutions are now first choice (15). While balanced crystalloid solutions were initially thought to prevent kidney injury (16), they do not clearly improve outcomes and may even be harmful for traumatic brain injury patients (17, 18).

2.2. Liberal vs restrictive fluid strategy

Optimizing tissue perfusion while preventing fluid overload can be highly challenging in critically ill invasively ventilated patients. A liberal fluid strategy often results in a positive cumulative fluid balance (CFB). A positive CFB is associated with worse outcomes in the ICU. For instance, CFB is associated with mortality and duration of

ventilation in invasively ventilated patients with the acute respiratory distress syndrome (ARDS) (19, 20). In critically ill patients with sepsis, a positive CFB is associated with mortality and kidney dysfunction (21-24). One meta-analysis of randomized clinical trials in critically ill sepsis patients in fact showed benefit of a restrictive fluid strategy combined with early deresuscitation following the resuscitation phase with respect to duration of ventilation and ICU length of stay (25).

2.3. Early vs late start of vasopressor therapy

Vasopressors are often used in conjunction with intravenous fluids to treat hypotension. Previously, vasopressor therapy was started only after 'sufficient' fluid administration and through a central venous route. Recent studies, however, suggest that an earlier start of vasopressor therapy leads to faster correction of hypotension, and prevents infusion of large volume of intravenous fluids (26-28). The 'Surviving Sepsis Campaign' guideline now recommends starting vasopressor therapy as soon as possible in hypotensive patients, even if it means administering it through a peripheral venous route (29). Herein, norepinephrine is the first choice vasopressor in most critically ill patients, due to a better safety profile compared to dopamine or epinephrine (30). Vasopressin can be added to norepinephrine when hypotension is refractory to initial therapy (31).

2.4. Geographic and geo-economic differences in fluid and vasopressor therapy

A large geographical variation in fluid therapy has been described. One study in 2014 showed that critically ill patients were most often prescribed albumin solutions in Australia, normal saline solutions in France and balanced solutions in Germany (32). In resource-limited ICUs certain types of fluids and vasopressors are given less often than in resource-rich ICUs due to differences in the supply chains, shortages and costs (33). While some colloidal solutions are no longer available for use in critically ill patients in the European Union, these harmful fluids might now be marketed in low- and middle-income countries (LMICs) (34). Last but not least, peripheral administration of vasopressors might be more common in LMICs due to the restricted use of central venous catheters.

2.5. Why this service review of fluid and vasopressor therapy?

Currently, we are uncertain how fluid and vasopressor therapy is practiced worldwide. Many aspects of fluid and vasopressor therapy have been challenged in recent years and critical care physicians remain highly divided on which approach is best (35), within and between countries (36). Furthermore, actual practice might be substantially

different from what is expected from the literature (36). The here proposed worldwide observational study in critically ill invasively ventilated patients on fluid and vasopressor therapy will provide a better insight in current and local practices, may show certain aspects of fluid and vasopressor therapy to have associations with clinical outcomes, and helps in the planning of future clinical trials in this field.

3. AIMS AND HYPOTHESES

3.1. Aims

To determine the current practice of fluid and vasopressor therapy in critically ill invasively ventilated patients (primary); to compare fluid and vasopressor therapy between Low- and Middle-income Countries (LMICs) and High-income Countries (HICs) and to determine the associations of various aspects of fluid and vasopressor therapy with clinical outcomes.

3.2. Hypotheses

There is large variation in fluid and vasopressor therapy in critically ill invasively ventilated patients (primary); there are differences in fluid and vasopressor therapy between LMICs and HICs; certain aspects of fluid and vasopressor therapy have an independent association with clinical outcomes.

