6.1.2. Secondary study parameters

- Time of start of vasopressors;
- Route of administration for vasopressors (i.e. central vs. peripheral route);
- Types of vasopressor used;
- Daily urine output;
- Cumulative fluid balance;
- Timing of start, type and infusion time (i.e. bolus vs. continuous infusion) of administered diuretic;
- Incidence of atrial arrhythmias;
- Incidence of acute respiratory distress syndrome (ARDS)
- Incidence of renal replacement therapy;
- Incidence of persistent renal dysfunction, defined as the need for renal replacement therapy at ICU discharge;
- ICU length of stay, defined as the time between ICU admission and discharge or death;
- Hospital length of stay, defined as the time between hospital admission and discharge or death;
- Duration of ventilation, defined as the time between initiation of invasive ventilation and successful liberation of ventilation.
- Ventilator-free days and alive at day 28, defined as 28 - x if successfully liberated from ventilation x days after initiation. If subject dies within 28 days ventilator-free days is set to 0;
- All-cause ICU mortality, defined as any death during ICU stay;
- All-cause in-hospital mortality at day 28, defined as any death during hospital stay before or on study day 28;
- All-cause in-hospital mortality at day 60, defined as any death during hospital stay before or on study day 60;
- All-cause in-hospital mortality at day 90, defined as any death during hospital stay before or on study day 90;

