- Heart rate, beats/min, at a convenient fixed time point;
- Atrial fibrillation or flutter during the last day, yes/no;
- Arterial or venous lactate, if measured, mmol/L , highest and lowest value;
- (Central) venous oxygen saturation ($S(c)VO_2$), mmol/L , if measured, highest and lowest value;
- Arterial partial pressure of oxygen (PaO_2), kPa or mmHg , at a convenient fixed time point;
 - (if no PaO_2 is known) Peripheral arterial oxygen saturation (SpO_2), percentage, at a convenient fixed time point;
- Inspired oxygen fraction, %, at time of PaO_2 or (if no PaO_2 is known) SpO_2 ;
- Suspected or confirmed infection that causes organ dysfunction (sepsis) yes/no;
- Was there new-onset (<7 days) respiratory symptoms, or acute worsening of respiratory symptoms?, yes/no, if yes;
- Are there bilateral opacities on chest imaging (including lung ultrasound), yes/no;
- If there was hypoxemia, was the hypoxemia explained by cardiac failure, yes/no?

- Richmond Agitation Sedation Scale (RASS), highest value of this day after intubation; and
- Sequential Organ Failure Assessment (SOFA) score.

C. Daily on day 1 and day 2;

- Type, volume, ml, and rate, ml/min, of each separate fluid infusion (including medication and parenteral nutrition);
- Type and volume of oral fluids;
- Anuria \geq 12 hours?, yes/no;
- Urine output, ml, over 24 hours;
- Extracorporeal life support, venoarterial/venovenous/no;
- Renal replacement therapy, yes/no, if yes;
 - Volume extracted by ultrafiltration, ml, over 24 hours;
- Cumulative fluid balance, ml;
- Loop diuretics given, yes/no, if yes;
 - Furosemide, yes/no, if no;
 - (if no furosemide used) Bumetanide, yes/no, if no;
 - (if no bumetanide or furosemide used) Torasemide, yes/no;
 - (if no Torasemide, bumetanide, furosemide used) Edecrin, yes/no;
 - Additional diuretic given (thiazide, carbonic anhydrase inhibitor or mineralocorticoid antagonist), yes/no;
- Serum creatinine, $\mu\text{mol/L}$ or mg/dL , at a convenient fixed time point;
- Serum hemoglobin, $\mu\text{mol/L}$ or mg/dL , at a convenient fixed time point;
- Serum albumin, at a convenient fixed time point;
- Vasopressors given, yes/no, if yes;
 - Time between ICU admission and initiation of vasopressors, only if not initiated on day 0, hours;
 - Drug(s) used as vasopressor;
- MAP, mmHg, at a convenient fixed time point;
- Heart rate, beats/min, at a convenient fixed time point;
- Atrial fibrillation or flutter during the last day, yes/no;

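### The data list records almost no chronic disease, so adjusted associations keep residual confounding and three incidence endpoints mix new with pre-existing disease

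*Protocol*

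**What the plan says.** Protocol section 3.2 states as its last hypothesis that "certain aspects of fluid and vasopressor therapy have an independent association with clinical outcomes". Section 5.5 plans logistic regression for mortality, "adjusting for a limited set of pre-specified confounders", and sizes the study for it "using the 10 event per variable rule of thumb": "we estimate to need 2500 patients to have 150 events in patients with ARDS".

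Section 6.2.3 itemises what is collected, in blocks A to F. The only item there that bears on chronic disease is a baseline creatinine, "lowest in the last year, if available".

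Section 6.1.2 lists "Incidence of atrial arrhythmias" among the secondary parameters, next to the incidence of renal replacement therapy (RRT) and of persistent renal dysfunction. The last is defined by RRT need when the patient leaves the ICU. The matching data items are plain daily answers, for example "Atrial fibrillation or flutter during the last day, yes/no". Section 5.3 excludes neither earlier atrial fibrillation (AF) nor chronic dialysis.

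**The concern.** Chronic cardiac, renal and hepatic disease plausibly influence how much fluid, diuretic and vasopressor a patient receives, and also whether the patient dies. The protocol's introduction (section 2.1) itself presents the patient's capacity to tolerate fluid as a guiding concept. If these conditions are not recorded, an association described as independent still carries whatever part of the effect belongs to them. An SAP can choose among collected variables; it cannot supply uncollected ones.

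The same omission reaches the endpoints. Incidence should count new disease. Without knowing who had AF or was on dialysis before admission, the counts include people whose condition predates the ICU stay.

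**Working it through.** **1. The plan's own figures.** Inputs from section 5.5: 150 events, ARDS incidence 20%, mortality 30%, 50 admissions per ICU, 25% ventilated for more than 24 hours, 10 events per variable.

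- Patients: 150 / (0.20 × 0.30) = 2500, as stated.
- ICUs: 2500 / (50 × 0.25) = 2500 / 12.5 = 200, as stated.
- Model terms: 150 / 10 = 15.

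These figures reproduce and are not in dispute.

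**2. Blocks A to F read against the hypothesis and the endpoints.**

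- Acute severity: SOFA, MAP, heart rate, lactate, oxygenation, creatinine, albumin, sepsis and admission reason are collected.
- Chronic disease: only the past-year creatinine, where available. The cardiac-failure question asks whether it explains current hypoxemia, so it is not a history item.
- New against old: the list asks for recent onset of respiratory symptoms, and block E asks whether AKI developed and on which day. AF and RRT carry no such qualifier.
- Pre-intubation rows (days -3 to -1) exist only for patients not yet ventilated at ICU admission.

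**3. Confounding by one unrecorded comorbidity.** The documents give no prevalence or risk ratio, so all inputs here are assumed. With prevalence p1 and p0 in the two exposure groups and mortality risk ratio RR, the bias factor is [1 + p1(RR − 1)] / [1 + p0(RR − 1)].

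| RR | 30% v 20% | 40% v 20% | 50% v 30% |
|---|---|---|---|
| 1.5 | 1.15/1.10 = 1.05 | 1.20/1.10 = 1.09 | 1.25/1.15 = 1.09 |
| 2.0 | 1.30/1.20 = 1.08 | 1.40/1.20 = 1.17 | 1.50/1.30 = 1.15 |
| 2.5 | 1.45/1.30 = 1.12 | 1.60/1.30 = 1.23 | 1.75/1.45 = 1.21 |

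If comorbid patients are instead concentrated in the low-exposure group, the factors invert, to between 1/1.23 = 0.81 and 1/1.05 = 0.95.

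**4. Pre-existing disease counted as incident.** With pre-existing share p and true new risk n among the rest, the counted proportion is p + (1 − p)n, and the pre-existing share of counted cases is p / [p + (1 − p)n]. Assumed ranges, before any clearing with the rows that are collected:

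- RRT, p 1–5%, n 5–15%: lowest share 0.01/0.1585 = 6%, highest 0.05/0.0975 = 51%. Of 2500 patients, 25 to 125.
- Atrial arrhythmia, p 5–15% (earlier AF that shows during the stay), n 5–15%: lowest share 0.05/0.1925 = 26%, highest 0.15/0.1925 = 78%. Of 2500 patients, 125 to 375.

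**5. Persistent renal dysfunction.** Suppose 4% of patients discharged from the ICU have a true new need and 1%, 3% or 5% were on dialysis before. The reported figure is then 5%, 7% or 9%, of which 1/5 = 20%, 3/7 = 43% or 5/9 = 56% is old disease.

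**6. Room in the model.** Six comorbidity terms plus age, SOFA and one exposure make 9, leaving 15 − 9 = 6 for admission reason and others. The sample size then stands. If the six came on top of a full set of 15, the rule would ask for 150 + 60 = 210 events, 210/0.06 = 3500 patients and 3500/12.5 = 280 ICUs.

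**The case against.** **Adjustment is far from empty.** Acute severity is a main driver of fluid and vasopressor use, and it is well covered. A reader might infer that the third hypothesis is wholly confounded and beyond repair. The documents do not support that: what remains is residual confounding by chronic disease. The factors in step 3 are also crude, and adjustment for correlated measured covariates may shrink them.

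**Old and new disease can be partly separated.** A reader might infer that the AF and RRT items cannot distinguish them at all. That goes too far. The day -3 to 0 rows, the day of AKI onset and the past creatinine all help. They still miss paroxysmal AF, dialysis not given on the day recorded, and patients without an earlier creatinine. Simply removing everyone with AF or RRT on those days would also discard true new cases that begin around intubation.

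**Some of this belongs in an SAP.** Naming the confounders and defining the at-risk set are ordinary SAP content, and section 8.2 promises one for each analysis. That is right, and neither is criticised here. The missing data items are a protocol matter.

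**LMICs against HICs.** A reader might infer that the comparison of LMICs and HICs is biased too. Section 3.2 frames it as a contrast of fluid and vasopressor practice, not of AF or RRT incidence, and nothing in the protocol says that chronic AF or dialysis differs between these settings. That inference is not made.

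**The primary aim is descriptive.** This is correct, and it limits the weight of the point.

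**Conclusion.** The point holds in a bounded form. The data list leaves the association hypothesis and the adjusted regression with residual confounding by chronic disease that an SAP cannot remove. For one comorbidity the assumed range is a factor of about 1.05 to 1.23 or its inverse, so the omission could create an apparent harm or hide a real one.

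Persistent renal dysfunction is the clearest case, because its definition takes in every chronic dialysis patient discharged from the ICU. For RRT and atrial arrhythmia, the shares in step 4 are what arises with no clearing at all; the collected rows would lower them by an amount the documents do not allow one to estimate. All prevalences, risks and risk ratios are assumptions. The omission itself is read directly from section 6.2.3. The primary endpoint and the sample size calculation are untouched.

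**What to change.** Add six yes/no items to block A of section 6.2.3, taken from the chart:

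- chronic heart failure;
- chronic kidney disease;
- chronic dialysis before admission;
- cirrhosis;
- earlier atrial fibrillation or flutter;
- treatment limitation at admission.

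Treat them as candidate confounders within the 15-term limit, so that the number of patients need not change. In section 6.1.2, report the incidence of RRT and of persistent renal dysfunction among patients without chronic dialysis, and the incidence of atrial arrhythmia among patients without earlier AF or flutter. Keep new onsets on day 0 in the count.

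The cost is a small transcription burden per patient and slightly smaller incidence denominators. The study stays within routinely recorded data.
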